Zimmer Biomet offers a Hip Screw technology that is capable of delivering a Bone Substitute Material (BSM) to the fracture-implant interface for fixation of fractures of the femoral neck [5][6]. This device allows hard setting BSM to the precise location, providing a multi-dimensional fixation that is critical to reduce the chance of joint collapse and articular fragment displacement and ultimately could reduce the high reoperation rates reported for this kind of injury.

This study will assess the reoperation rates, including revision, and document the clinical and radiographic outcomes of hip fracture patients, utilizing the N-Force Fixation System. Results will be compared to “standard” non-augmented cannulated screw (historic control).

IV. Study Objectives

The objective of this prospective study is to assess safety and performance of N-Force Screws augmented with N-Force Blue applied in intracapsular proximal femur fracture treatment. Further results will be compared to non-augmented standard cannulated screws (historic control).

Safety: Will be assessed by monitoring the frequency and incidence of adverse events (AE), serious adverse events (SAE), adverse device effects (ADE), serious adverse device effects (SADE), and unanticipated serious adverse device effects (USADE) and device deficiencies.

Performance: Will be determined by analyzing the fracture healing (union) rate at 6 weeks, 3 months, 6 months, and 12 months postoperatively.

The primary endpoint of this study is defined as re-operation within 12 months after initial surgery. Reoperation is defined as a second surgery to correct the previous procedure or the complications of a previous surgery. For this study, reoperation will include second surgeries to promote fracture healing, relieve pain, treat infection, or improve function including:

- Removal of the implant prior to fracture healing
- Internal fixation with another implant during revision surgery
- Revision to total hip arthroplasty
- Incision and drainage or other soft tissue procedure due to deep infection at the bone implant interface.

Secondary endpoints of this study include:

- Clinical (FIX-IT) and radiologic (RUSH)^{[8][9]} fracture healing at 6 weeks, 3, 6 and 12 months post-surgery.
- Length of femoral neck ^{1.a.[7]}
- Proportion of patients with avascular necrosis at one year FUP (Steinberg classification)
- Functional Index for Trauma (FIX-IT)^[10]
- Harris Hip Score^[11]
- Timed “Up-And-Go” Test^[12]
- EQ-5D-5L

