5. EQ-5D-5L
6. FIX-IT
7. Timed “Up and Go” Test
8. Harris Hip Score
9. Adverse Event Reports(s) (as applicable)
10. Protocol Deviation(s) (as applicable)
11. Implanted Device Form (as applicable)
12. Study Completion (as applicable)

Subjects will be followed post-operatively for 12 months. Unless the study is otherwise closed, data will continue to be collected until the subject completes the study per the protocol, voluntarily withdraws from the study, is withdrawn from the study by the investigator, is lost to follow-up, undergoes revision to remove a study device (due to complication), or expires. See Management of Incurrent Events (Section IX, Subsection D of this protocol) for additional details. Reason(s) for study completion must be documented on the Study Completion case report form.

L. Minimization of Subjects Lost to Follow-up

Subject follow-up is extremely important for the conduct of a clinical study, and the expectation is to maintain the highest possible rate of follow-up compliance throughout this study. During the informed consent process and at each follow-up interval, subjects should be counseled on the importance of completing future study follow-up intervals.

M. Radiographic Definitions and Methods

All postoperative radiographic evaluations performed according to the protocol will be reviewed by the Investigator at the time of the evaluation and documented using the **Physician Assessment of Post-op Radiographs** case report form. This includes documentation of any significant radiographic findings. In addition, an **Adverse Event** case report form must be completed for those findings indicated by an asterisk on the **Physicians Assessment of Post-op Radiograph** case report form, or for any other findings identified as an adverse event.

[figure not shown]
o **Method to derive the length of the femoral neck:**

1. Draw a line along the femoral shaft axis.
2. Draw a line along the femoral neck axis.
3. Measure the distance CD (blue line) in millimeter.
4. Measure the distance AB (red line) of the **inferior** screw in millimeter.

[figure not shown]
To adjust for x-ray magnification the actual length of the femoral neck will be calculated using the following formula:

$$\text{Length of the femoral neck [mm]} = CD_{\text{measured}} \times \frac{AB_{\text{true}}}{AB_{\text{measured}}}$$

$$AB_{\text{true}} = \text{Known screw length [mm]}.$$

[figure not shown]

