In the event that removal of one or more of the study related components is necessary (due to complication), the Investigator will determine the best treatment and/or revision method for the subject.

Prior to revision surgery, the Investigator or qualified Designee must document any significant radiographic findings related to the need for revision on the **Physician Assessment of Postop Radiographs** case report form. An **Adverse Event** case report form must be completed for those findings indicated by an asterisk on the **Physicians Assessment of Postop Radiograph** case report form.

Once the revision surgery has been completed, the Investigator or qualified Designee must complete an **Adverse Event Report** case report form as well as a **Study Completion** case report form terminating the subject from the study. For the study completion status, select “Study Device Removed”. This procedure also applies to partial revisions e.g. removal of one of the three screws.

4. Investigator Withdrawal

The Investigator can choose to withdraw a subject from the study if the subject no longer meets study inclusion/exclusion criteria. The reason for the Investigator’s withdrawal of the subject must be documented on the **Study Completion** case report form.

5. Subject Withdrawal

Study subjects may choose to withdraw from the study at any time, for any reason. If possible, a final evaluation will be completed for any subject who no longer wishes to participate in the study. The reason for the subject withdrawal must be documented on the **Study Completion** case report form.

6. Lost to Follow-up

A study subject will be considered lost to follow-up after they have missed a visit and a reasonable number of attempts to locate and evaluate them have failed. All attempts to contact the subject are to be documented in the subject's medical record and on the **Study Completion** case report form. In particular, the reason for the Study Completion must be documented. Missed visit(s) also must be documented using the **Protocol Deviation** case report form, unless the visit is retrospective.

7. Protocol Deviations

Investigators should not deviate from the study protocol. If a protocol deviation does occur, the deviation must be documented on the **Protocol Deviation** case report form and submitted to the Sponsor. If applicable per their reporting requirements, the Investigator or Designee will also report applicable protocol deviations to their IRB or EC.

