8. Study Termination

Study subject participation is expected to end upon completion of the subject's one year follow-up visit unless the subject voluntarily withdraws from the study, is withdrawn from the study by the Investigator, is lost to follow-up, undergoes revision to remove a study device (due to complication), or expires. Reason(s) for study completion must be documented on the **Study Completion** case report form.

If the Sponsor decides to terminate the study early, the Sponsor will inform the Investigators of the reason for early study termination. It is the responsibility of the Investigators to inform their IRB or EC as applicable according to local and national laws/regulations.

9. Modification of the Protocol

All amendments to this clinical protocol shall be agreed to by the Sponsor and be recorded with a justification for the amendment prior to implementation. Approval of the applicable IRB or EC must be obtained prior to implementation, if required according to the local and/or national

laws/regulations.

E. Medical Events/Adverse Events Definitions and Classifications

An adverse event is any unfavorable or unintended sign, symptom, or disease that impacts the subject. Adverse event is synonymous with complication or medical event.

Adverse events are required to be reported on the **Adverse Event Report** case report form. The completed **Adverse Event Report** case report form must be submitted to the Sponsor in a timely manner. The Investigator or Designee will also promptly provide the Sponsor with any additional requested information required for the Sponsor to comply with regulatory requirements. If applicable per their reporting requirements, the Investigator or Designee will also report applicable adverse event(s) to their IRB or EC.

The following definitions are from ISO 14155:2011.

1. Classification of the Event

Adverse Event (AE):

An adverse event is any untoward medical occurrence, unintended disease or injury, or untoward clinical signs (including abnormal laboratory findings) in subjects, users or other persons, whether or not related to the investigational medical device.

Note 1: This definition includes events related to the investigational device or the comparator.

Note 2: This definition includes events related to the procedures involved.

Note 3: For users or other persons, this definition is restricted to events related to investigational medical devices.

Serious Adverse Event (SAE)⁽ⁱ⁾:

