for intracapsular femur fractures, 151 evaluable subjects will be required at 12 months follow-up to show necessary statistical improvement from the historical revision rate. With an expected lost to follow-up rate of 20%, 190 subjects will be required for this clinical study. The assumed reoperation rate for the N-Force Screws augmented with N-Force Blue is 7.5%.

XII. Quality Control & Quality Assurance

The study is conducted in accordance with the Declaration of Helsinki and the ISO 14155:2011.

The Investigator will be required to permit representative(s) of the Sponsor's monitoring team to inspect all Case Report Forms and corresponding sections of the study patients office records and/or hospital original medical records. These audits will be done for quality assurance purposes, i.e. verifying adherence to the Clinical Investigation Plan and the completeness and accuracy of the data being entered on the Case Report Forms.

The Clinical Investigation Plan will be provided to all participating study centers. The Investigators will be fully trained in the proper reporting and submission of trial data prior to patient enrolment. Completed Case Report Forms will be reviewed before entering the data into a central database by the Sponsor.

The Clinical Study Manager is responsible for generating data queries for missing or unclear data if needed. It is the responsibility of the Clinical Study Manager to ensure data quality.

There are regular meetings between the Investigators and Zimmer Biomet Clinical Affairs staff. Written correspondence to all sites is used to inform the Investigators of routine study details and to update them on study status.

XIII. Suspension or Premature Termination of the Clinical Investigation¹

Sponsor may suspend or prematurely terminate clinical investigation site(s) or entire clinical investigation for significant and documented reasons. If suspension or premature termination occurs at an individual investigation site, sponsor shall inform the responsible regulatory authority(s) as appropriate and ensure that ethic committee(s) are notified. If the suspension or premature termination was in the interest of safety, the sponsor shall inform all other principal investigators. If suspension or premature termination occurs,

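### The loss-to-follow-up rule can end planned data collection after one missed visit and failed contact attempts, with no later check for reoperation inside the 12-month endpoint window

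*Combined protocol and SAP*

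**What the plan says.** Section IV sets the endpoint: "The primary endpoint of this study is defined as re-operation within 12 months after initial surgery". Follow-up visits fall at 6 weeks, 3, 6 and 12 months.

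Section IX.D.6 (Lost to Follow-up) defines a lost subject as one "considered lost to follow-up after they have missed a visit and a reasonable number of attempts to locate and evaluate them have failed". It gives no number of attempts. Attempts and reason go on the Study Completion form: "In particular, the reason for the Study Completion must be documented". Missed visits are recorded separately as protocol deviations, except retrospective ones.

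Two sections make loss an end point for follow-up:

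- Section VIII.K: "data will continue to be collected until the subject completes the study per the protocol" or until one of several other things happens. The list includes that the subject "is withdrawn from the study by the investigator, is lost to follow-up, undergoes revision to remove a study device (due to complication), or expires".
- Section IX.D.8: "Study subject participation is expected to end upon completion of the subject's one year follow-up visit unless the subject voluntarily withdraws from the study", followed by the same exceptions, loss among them.

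Section XI.B plans for this loss: "With an expected lost to follow-up rate of 20%, 190 subjects will be required for this clinical study". It requires 151 evaluable subjects at 12 months. Section XI.A plans descriptive summaries and gives no rule for analysing lost subjects.

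**The concern.** The stopping rule is built around visits, while the primary endpoint is an event. Radiographic scores and the Harris Hip Score need the subject to attend. A second operation does not: it can be established from records or a telephone call. Under these sections an early missed visit with unsuccessful attempts closes the planned search for that event while most of the endpoint window is still to run.

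In this population a missed visit may be linked to the outcome, for example through readmission, surgery at another hospital, lost mobility or death. The comparator is a fixed historical rate, so no concurrent arm shares the same loss. If subjects who drop out of sight have more reoperations than those who stay, the observed rate is too low and the comparison leans towards the device.

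**Working it through.** **1. The plan's own figures.** Section XI.B gives a historical rate p0 = 0.15, an assumed device rate p1 = 0.075, 151 evaluable and 190 enrolled. It does not state alpha or power. Assuming two-sided 0.05 and 80% power:

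n = [(1.96 × √(0.15 × 0.85) + 0.8416 × √(0.075 × 0.925)) / 0.075]² = 150.97, so 151.

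Allowing for 20% loss, 151 / 0.8 = 188.75, so 189, close to the stated 190. The arithmetic reproduces and does not depend on the loss rule. The allowance leaves 190 − 151 = 39 subjects without 12-month status.

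**2. Endpoint time left unobserved.** Visit windows come from Section II; 3 months is taken as 91 days and 6 months as 183.

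| Visit missed | Window closes | Days left to day 365 |
|---|---|---|
| 6 weeks (± 14 days) | 42 + 14 = 56 | 309 |
| 3 months (± 30 days) | 91 + 30 = 121 | 244 |
| 6 months (± 60 days) | 183 + 60 = 243 | 122 |

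These are upper limits if loss is declared no earlier than the window's close. Time spent on contact attempts shortens them.

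**3. All-subject rate under assumed rates in the lost.** With 7.5% in the 151 and an assumed rate q in the 39, the rate is (151 × 0.075 + 39q) / 190:

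| q (assumed) | Reoperations | All-subject rate |
|---|---|---|
| 7.5% | 14.25 | 7.5% |
| 15% | 17.18 | 9.0% |
| 22.5% | 20.10 | 10.6% |
| 30% | 23.03 | 12.1% |

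**4. Tipping point (exact 95% intervals).** Take 11/151 = 7.3%, near the assumed rate. The upper limit is 12.7%, below 15%. Adding 7 reoperations among the 39 gives 18/190 = 9.5%, upper limit 14.6%. Adding 8 (8/39 = 20.5%) gives 19/190 = 10.0%, upper limit 15.2%, which no longer excludes 15%.

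**5. Chance of a false improvement.** Assumptions: 190 enrolled, 38 lost (20%) and excluded, true overall rate 15%, exact one-sided test at 0.025 on n = 152, which rejects at 14 or fewer events. If the lost have r times the rate of the retained, the retained rate is 0.15 × 190 / (152 + 38r):

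| r (assumed) | Rate in retained | Chance of false improvement |
|---|---|---|
| 1 | 15.0% | 2.4% |
| 1.5 | 13.6% | 6.5% |
| 2 | 12.5% | 13.3% |
| 3 | 10.7% | 33.0% |

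With r = 1 there is no bias, only lower precision. Steps 3 to 5 describe the whole 20% allowance, not the part of it caused by this rule.

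**The case against.** A reader might infer that one missed visit permanently removes a subject and that later reoperations go uncounted. The documents do not say so. A missed visit alone does not close a subject: attempts must also fail, and missed visits are already recorded as deviations. No passage forbids reinstatement or tells the site to disregard an event learned later. Section IX.D.2 requires serious, femur-related and unanticipated events to be reported, with no cut-off at loss.

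It is also tempting to read the failed attempts to both locate and evaluate as covering a subject who is reached but cannot attend. That reading is possible, but IX.D.6 goes on to speak of attempts to contact, and a site that reaches someone by telephone would not naturally call them lost.

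Nor is there support for saying that the rule raises loss above 20%, since the plan does not say which definition that figure assumes. Many of the 39 might be unreachable under any rule. Section VIII.L states an expectation of high compliance and asks for counselling at each interval, and the exclusion criteria remove patients expected to have follow-up problems or not to survive the schedule.

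All of this stands and limits the claim. It does not close the gap. The reporting duty covers events that come to the site's attention, but nothing sends the site to find them once the subject is declared lost.

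**Conclusion.** The point holds as a gap in ascertainment of the primary endpoint. Section IX.D.6 with VIII.K and IX.D.8 is a stated stopping rule, not merely missing detail. After it applies, the plan provides no re-contact at later visits, no 12-month check for reoperation, serious adverse events or death, and no procedure for a subject who returns.

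The unobserved time per affected subject is up to about 309 days. Any bias would favour the device if loss is positively related to reoperation; its size cannot be determined from the documents. The 7.5% to 12.1% range, the tipping point and the false-improvement figures rest on assumed rates in lost subjects and illustrate total loss only. They show that loss on the planned scale could matter, not that this rule causes it. The change is a worthwhile, cheap improvement.

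**What to change.** Amend IX.D.6, with matching edits to VIII.K and IX.D.8:

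- A subject who misses a visit and cannot be reached stays active and is re-contacted at each later visit. Data are collected if they return.
- Lost to follow-up is entered on the Study Completion form only after the 12-month window closes (365 + 90 = day 455).
- Before that entry, the site makes one final check, as far as consent allows: its own records and a contact attempt, covering reoperation (date and type), serious adverse events and vital status to day 365.

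The cost is a short amendment to three sections, about one extra call or records check per missing subject (at most about 39 at the planned loss rate), and later close-out of those files. A close-out year is already planned. The consent text was not available, so whether it permits these checks needs confirming first.

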II. Appendices:.....	33

I. Study Synopsis

Study Title	N-Force Screws augmented with N-Force Blue in Intracapsular Proximal Femur Fracture Treatment
Abbreviated Study Title	N-Force Study
Sponsor	Zimmer Biomet, Warsaw, Indiana
Protocol Number	CMU2017-60T
Anticipated Start Date	Q4 2018
Study Objectives	
The objective of this prospective study is to confirm safety and performance of N-Force Screws augmented with N-Force Blue applied in intracapsular proximal femur fracture treatment.
 
Further results will be compared to non-augmented standard cannulated screws (historic control).
 
Primary Endpoint:
 
 • Re-operation within 12 months after initial surgery to promote fracture healing, relieve pain, treat infection, or improve function^[4]. 
Secondary Endpoints:
 
 • Radiographic and clinical fracture healing of the proximal femur using standard scoring methods and patient satisfaction. • Cost effectiveness
Target Population	Patients with primary Garden I and II intracapsular proximal femur fractures requiring surgical intervention and eligible for fixation by three cannulated screws augmented with N-Force Blue.
Study Design	Multicenter, prospective, non-controlled clinical study
Study Type	Post-market clinical follow-up study (PMCF)
Sample Size	190 Subjects (151 + 20% anticipated lost to follow-up)
Length of Study	3 years (1 year enrollment, 1 year follow-up and 1 year study close-out)
Follow-up Intervals	6 weeks, 3 months, 6 months and 12 months after surgery
Inclusion/Exclusion Criteria	
Inclusion Criteria:
 
 • Patient has primary Garden I or II intracapsular proximal femur fracture requiring surgical intervention and is eligible for fixation by three cannulated screws augmented with N-Force Blue.

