A Serious Adverse Event is any adverse event that

- a. led to death
- b. led to serious deterioration in the health of the subject, that either resulted in:
 1. a life-threatening illness or injury, or

2. a permanent impairment of a body structure or a body function, or
3. in-patient or prolonged hospitalization, or
4. medical or surgical intervention to prevent life-threatening illness or injury or permanent impairment to a body structure or a body function

- c. led to fetal distress, fetal death or a congenital abnormality or birth defect.

Note: Planned hospitalization for a pre-existing condition, or a procedure required by the protocol, without serious deterioration in health, is not considered a serious adverse event.

Adverse Device Effect (ADE)⁽ⁱ⁾:

An Adverse Device Effect is an adverse event related to the use of a medical device.

Note 1: This definition includes adverse events resulting from insufficient or inadequate instructions for use, deployment, implantation, installation, or operation, or any malfunction of the medical device.

Note 2: This definition includes any event resulting from use error or from intentional misuse of the medical device.

Serious Adverse Device Effect (SADE)⁽ⁱ⁾:

A Serious Adverse Device Effect is an adverse device effect that has resulted in any of the consequences characteristic of a serious adverse event.

The Sponsor is responsible for determining the final classification of adverse events.

If an Unanticipated Serious Adverse Device Effect (USADE) is identified by the Sponsor, it will be promptly reported to concerned Investigators and regulatory authorities as required by applicable regulatory requirements. If applicable per their reporting requirements, the Investigator or Designee will report the USADE to their IRB or EC.

Device Deficiency:

A Device Deficiency is defined as an inadequacy of medical device with respect to its identity, quality, durability, reliability, safety or performance.

2. Intensity of Symptoms

Mild:

The subject is aware of the sign or symptom, but finds it easily tolerated. The event is of little concern to the subject and/or little clinical significance. The event is not expected to have any effect on the subject's overall health or well-being.

Moderate:

The subject has discomfort enough to cause interference with or change in usual activities. The event is of some concern to the subject's health or well-being and may require medical intervention and/or close follow-up.

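### The sponsor, which supplies the device, sets the final class of every adverse event, and the plan does not require the investigator's classification to be kept or shown beside it

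*Combined protocol and SAP*

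**What the plan says.** Section IX.E.1 defines AE, SAE, ADE and SADE and then adds, with no exception by type of event: "The Sponsor is responsible for determining the final classification of adverse events".

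The safety objective in Section IV rests on these classes: "Will be assessed by monitoring the frequency and incidence of adverse events (AE), serious adverse events (SAE), adverse device effects (ADE"), followed by "serious adverse device effects (SADE), and unanticipated serious adverse device effects (USADE) and device deficiencies". That makes six measures.

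Whether an event enters the device-effect classes turns on a judgement of relation: "An Adverse Device Effect is an adverse event related to the use of a medical device". Section IX.E gives no causality scale or criteria for it. Escalation also starts from the sponsor's view: "If an Unanticipated Serious Adverse Device Effect (USADE) is identified by the Sponsor, it will be promptly reported to concerned Investigators".

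The synopsis names the sponsor as "Zimmer Biomet, Warsaw, Indiana", and Section III shows that it supplies the device: "Zimmer Biomet offers a Hip Screw technology that is capable of delivering a Bone Substitute Material (BSM"). The synopsis also assigns the statistical analysis to the sponsor or its designee.

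**The concern.** The party with an interest in the result has the final say on seriousness, device relation and expectedness, and the plan does not say what happens when the treating surgeon disagrees. Section V describes a non-controlled study, so there is no concurrent arm classified by the same people under the same rule against which a shift could be seen.

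The ADE, SADE and USADE rates are at stake. Section XI says that the descriptive summaries may support regulatory submissions and publications. A reader of those summaries could not tell whether the device-effect rates reflect the investigators' assessments, the sponsor's, or a mixture, nor how many events changed class.

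**Working it through.** The point is mainly one of reading, so the relevant sections are set side by side first.

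**1. Is the final-classification rule limited anywhere?**
- Section IX.E.1 states it without exception.
- Sections IX.D.2 and IX.E require the site to submit an AE report form. They do not say whose class is tabulated.
- Section XI.A specifies counts, percentages and 95% CIs for categorical data. It is silent on which classification feeds them, so the final one applies by default.
- No event adjudication committee or data monitoring committee is described.
- The only independent review mentioned (Sections II, V and VIII.M.2) concerns radiographs and is at the sponsor's option.

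**2. Which results depend on the classification?**

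| Measure | Changed if device relation is changed? | Changed if seriousness is changed? |
|---|---|---|
| Total AE | No | No |
| SAE | No | Yes |
| ADE | Yes | No |
| SADE | Yes | Yes |
| USADE | Yes (also by expectedness) | Yes |
| Reoperation within 12 months | No | No |

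The last row follows from Section IV, which defines the primary endpoint by the second surgery performed, not by an AE class.

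**3. What record of the investigator's view remains?**
- The AE report form (Sections IX.D.2 and IX.E).
- For device-related events, a Product Experience Report sent within 7 days with supporting documents (Section II, table footnote).
- Reports to the IRB or EC where its rules require them.
- A requirement that form data agree with source or that differences be explained (Section IX.B.3).

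These keep a site-level trail. No section carries it into the safety tables.

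**4. Illustration of size.** The documents give no expected number of device effects, so the counts below are assumptions. The denominator is the 190 planned subjects (Section XI.B). The rate is x/190, with an exact (Clopper-Pearson) 95% CI.

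| Assumed subjects with an investigator-rated ADE | Rate (95% CI) | Assumed number reclassified | Rate after (95% CI) |
|---|---|---|---|
| 10 | 5.3% (2.6 to 9.5%) | 3 | 7/190 = 3.7% (1.5 to 7.4%) |
| 6 | 3.2% (1.2 to 6.7%) | 2 | 4/190 = 2.1% (0.6 to 5.3%) |

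The relative falls are 3/10 = 30% and 2/6 = 33%. Reclassification upward would move the rates the other way. At counts this small, two or three judgement calls change the point estimate by about a third, although the intervals overlap widely.

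The plan states no device-effect rate that could be reproduced. Its one design calculation, 151 evaluable subjects, concerns reoperation and does not bear on this point.

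**The case against.** Sponsor review of event classes is legitimate. It can correct a site's misreading of the definitions, and it can move events upward as well as downward. Reporting is descriptive, with no device-effect threshold or test, so no formal decision turns on a shift. The case report forms in Appendix B are not shown and may already record the investigator's ratings of seriousness and relation. All of this stands. It limits the weight of the point but does not answer it, because a rating held on a form is still not one that the plan says will be reported.

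A reader might infer three stronger things that the documents do not support:

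- **That a reclassified event disappears entirely.** It does not. The AE form, the Product Experience Report and the source records remain. Device removal and reoperation of the hip are also separate outcome categories (Section IX.E.3), and a revision must be recorded on its own Study Completion form (Section IX.D.3).
- **That the ADE, SADE and USADE counts make up the whole safety result.** They are three of six measures, and the total AE count does not move with any reclassification.
- **That the sponsor should be barred from downgrading.** The gap is one of disclosure. A one-way rule would build in an upward bias and prevent correction of genuine site errors.

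Nothing in the text suggests an intent to reclassify downward.

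**Conclusion.** The point holds as a gap in transparency. Final classification rests with the supplier of the device, and no section requires the investigator's classification to be kept in the analysis or differences to be reported. The ADE, SADE and USADE rates, and the identification of USADEs, therefore rest on the sponsor's judgement in a single-arm study, and the reported tables need not show where it departs from the investigators'.

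The documents do not allow the effect to be sized. On the assumed counts it is 1 to 2 percentage points (3.2% to 2.1%; 5.3% to 3.7%). It should be corrected because the remedy is cheap, but it does not threaten the primary endpoint. The conclusion assumes that Appendix B contains no rule on reporting both classifications.

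**What to change.** Add to Section IX.E.1 that the investigator's and the sponsor's classifications of seriousness, device relation and expectedness are both recorded and retained. Add to Section XI.A that ADE, SADE and USADE rates with 95% CIs are tabulated side by side under each classification, and that every disagreement is listed in the report with its reason.

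The sponsor keeps its review role and may reclassify in either direction. The change concerns reporting only and leaves the notification procedure as written. The listing would show afterwards any event that the investigator, but not the sponsor, placed in the USADE class.

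Cost: one extra table and one listing, plus a data field if the AE form lacks the investigator's rating. It needs no additional subjects, visits or committee. The device-effect rates may look slightly less favourable under the investigator's classification.
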